## 11.2 Adverse Events

Adverse events will be coded using the Medical Dictionary for Regulatory Activities (MedDRA) version 21.0 or higher. TEAEs are defined as AEs started after the start of the first infusion of IMP. All AEs regardless of when they were reported will be listed.

In addition to an overall TEAE analysis, the analysis will be repeated for each period. An AE will be counted in the respective analysis, if the onset of the event falls within the period. For the definition of start and end of the periods see [Table 8](#) and [Table 9](#).

- An overview summary of TEAEs, including number of subjects, percentages of subjects, the number of events, and TEAE rate per time at risk, including the following. This summary will also be provided for the subgroup of Japanese subjects and by age group (<65 year, ≥65 years):
  - Any TEAE
  - TEAEs related to IMP
  - TEAEs related to corticosteroid treatment

- Temporally associated TEAEs (defined as an AE with an onset between the start of the IMP infusion and up to 72 hours after the end of IMP infusion)
  - Related TEAEs or temporally associated TEAEs to IMP
  - TEAEs leading to permanent discontinuation of IMP
  - TEAEs leading to withdrawal from study
  - TEAEs leading to IMP dose interruptions
  - AESIs
  - AESIs related to IMP
  - Temporally associated AESIs (defined as an AESI with an onset between the start of the IMP infusion and up to 72 hours after the end of IMP infusion)
  - Serious TEAEs
  - Serious TEAEs related to the IMP
  - Serious TEAEs related to corticosteroid treatment
  - Temporally associated serious TEAEs
  - Fatal serious TEAEs
- 
- The following descriptive tables will be generated for TEAEs, including number of subjects, percentages of subjects, the number of events, and TEAE rate per time at risk. Analyses marked with \* will also be provided for the subgroup of Japanese subjects:
    - TEAEs by System Organ Class (SOC) and Preferred Term (PT)  
Note: This table will also be provided by age group (<65 year,  $\geq$ 65 years)
    - TEAEs by SOC, PT, and maximum severity\*
    - Causally related TEAEs by SOC and PT\*
    - Temporally associated TEAEs by SOC and PT\*
    - Causally related TEAEs or temporally associated TEAEs by SOC and PT
  
  - All AE summaries presented by SOC and preferred term will include a virtual SOC comprising of local reactions, ie, all AEs reported within the MedDRA High level terms “Administration site reactions NEC” or “Infusion site reactions” or “Injection site reactions”. Local reactions will be analyzed by using a virtual SOC called “local adverse events”.

- All AE summaries presented by SOC and preferred term will include a virtual SOC “Thromboembolic Events” comprising all AEs reported within the MedDRA SMQs in Section 11.3.

All tables will be displayed in descending order of total incidence by preferred term and by SOC and PT, respectively.

TEAE rates per time at risk will be calculated as annualized TEAE rates using:

$$\text{Annualized TEAE rate} = \frac{\text{number of events}}{(\text{Total observational time in this period (days)} / 365.25)}$$

Number of events and total observational time are counted within the respective period and treatment group. Start dates and end dates to derive the observational time for the respective periods are defined in [Table 8](#) and [Table 9](#).

Temporally associated TEAEs are defined as AEs with an onset between the start of the infusion and up to 72 h after the end of IMP infusion. In case time of onset of AE is missing, the AE is considered temporally related, if the onset of the AE is between the day of the start of infusion and the day of the end of infusion + 3 days (inclusive).

The following listings will be provided:

- All Adverse Events
- All serious TEAEs

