#### 10.4.3 Safety Analyses

All Safety analyses will be performed separately by treatment sequence based on the SAF, SAF-Ex and overall. Adverse events will be coded using MedDRA version 22.0 or higher. TEAEs are defined as AEs reported at or after the start of study treatment. All AEs regardless of when they were reported will be listed.

- An overview summary of TEAEs, including frequency counts and percentages of subjects and the number of events and TEAE rate per time at risk, including the following:
  - Any TEAE
  - TEAEs related to IMP
  - TEAEs related to corticosteroid treatment
  - Temporally associated TEAEs (defined as an AE with an onset between the start of the IMP infusion and up to 72 hours after the end of IMP infusion)

- Related TEAEs or temporally associated TEAEs to IMP
- TEAEs leading to permanent discontinuation of IMP
- TEAEs leading to withdrawal from study
- TEAEs leading to IMP dose interruptions
- AESIs
- AESIs related to the IMP
- Temporally associated AESIs (defined as a AESI with an onset between the start of the IMP infusion and up to 72 hours after the end of IMP infusion)
- Serious TEAEs
- Serious TEAEs related to the IMP
- Serious TEAEs related to corticosteroid treatment
- Temporally associated serious TEAEs (defined as a serious TEAE with an onset between the start of the IMP infusion and up to 72 hours after the end of IMP infusion)
- Fatal serious TEAEs
- TEAEs will be summarized by severity. In addition, the frequency counts and percentage of AEs will be summarized in descending order of total incidence by preferred term (PT) only and by system organ class (SOC) and PT. The following descriptive tables will be generated for TEAEs, including frequency counts and percentages of subjects and the number of events and TEAE rate per time at risk:
  - TEAEs by SOC and PT
  - TEAEs by SOC, PT, and maximum severity
  - Causally related TEAEs by SOC and PT
  - Temporally associated TEAEs by SOC and PT
  - Causally related TEAEs or temporally associated TEAEs by SOC and PT

The following safety parameters will be analyzed descriptively:

- Hemolysis, suspected or confirmed
- Wells' Criteria score for DVT

- Wells' Criteria score for PE
- Laboratory safety parameters
- Vital signs
- Physical examination

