### Adverse Events

Imputations in the adverse events dataset are used for slotting events to the appropriate study time periods and for sorting in data listings. They will not be used to calculate duration of AEs. If an AE start or end date is missing, then the duration of the AE will be set to missing.

As a rule, the missing start date elements will be imputed with following priorities:

1. The event is counted as TEAE for IgPro20 with the earliest onset possible.
2. The event is counted as TEAE for Placebo with the earliest onset possible.

In Sequence B, if due to missing elements the event qualifies to either IgPro20 or Placebo, the event is assigned to be treatment-emergent in the IgPro20 period.

If the AE with missing start date elements is related to oral corticosteroid treatment the imputed start date must not be before the start date of the oral corticosteroid treatment.

Date	Missing Element	Rule
Start Date	day, month, and year	
Do not impute completely missing AE start dates.
 
Sequence A
 
 
• The AE will be deemed treatment-emergent in Study Period 1 (Week 1-25) if the AE end date does not indicate that the AE ended prior to IMP start date (week 1),
 
• otherwise the AE will be deemed not treatment-emergent.
 
 
Sequence B
 
 
• The AE will be deemed treatment-emergent in Study Period 2 (Week 25-53) if the AE end date does not indicate that the AE ended prior to IMP start date (week 25),
 
• else the AE will be deemed treatment-emergent in Study Period 1 (Week 1-25) if the AE end date does not indicate that the AE ended prior to IMP start date (week 1),
 
• otherwise the AE will be deemed not treatment-emergent.
 

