Start Date	day, month only	
Sequence A
 
 
• If the year of AE start date is the same as the year of IMP start date (week 1), and the AE end date indicates the AE ended after IMP start date (week 1), then set AE start date to IMP start date (week 1),
 
• otherwise set AE month and day to January 1st
 
 
Sequence B
 
 
• If the year of AE start date is the same as the year of IMP start date (week 25), and the AE end date indicates the AE ended after IMP start date (week 25), and IMP start date (week 25) is not missing then set AE start date to IMP start date (week 25),
 
• else if the year of AE start date is the same as the year of IMP start date (week 1), and the AE end date indicates the AE ended after IMP start date (week 1) then set AE start date to IMP start date (week 1),
 
• otherwise set AE month and day to January 1st
 
 
Oral corticosteroid treatment
 
If the AE is related to oral corticosteroid treatment take the later date of first oral corticosteroid treatment start date and the date imputed to the rules in “Sequence A” or “Sequence B” above.

	day only	
Sequence A
 
 
• If the month/year of AE start date is the same as the month/year of IMP start date (week 1), and the AE end date indicates the AE ended after IMP start date (week 1) then set AE start date to IMP start date (week 1),
 

Date	Missing Element	Rule

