### 8.3.1 Study Time Periods for Adverse Events

Adverse events (AEs) with onset date/ time after start of first infusion of IMP are TEAEs. Assessment whether an AE is considered treatment-emergent, will take place after imputation of partially missing dates (see Section 8.1.2).

The TEAE analysis will be done for the periods and groups shown in Section 11. An AE will be counted for the analysis of a period if the onset of the event falls within the period. For the definition of start and end of the periods see [Table 8](#) and [Table 9](#).

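### The SAP's TEAE boundary (onset after the first infusion starts) differs from the protocol's (at or after), conflicts with its own date imputation, and leaves first-day AEs without an onset time undetermined

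*SAP*

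**What the plan says.** Protocol section 10.4.3: "TEAEs are defined as AEs reported at or after the start of study treatment". The boundary is inclusive, and the verb is *reported*.

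SAP section 11.2: "TEAEs are defined as AEs started after the start of the first infusion of IMP". SAP section 8.3.1: "Adverse events (AEs) with onset date/ time after start of first infusion of IMP are TEAEs". Both are strict, and both refer to when the AE began. SAP section 5 states that nothing planned in the protocol was changed.

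On order of operations, SAP section 8.3.1 says: "Assessment whether an AE is considered treatment-emergent, will take place after imputation of partially missing dates". The AE rules in SAP section 8.1.2 treat two situations differently:

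- **Partial start date.** If the known month and year (or the year alone) match the first infusion and the AE ended after it, "then set AE start date to IMP start date (week 1". The first stated priority is "The event is counted as TEAE for IgPro20 with the earliest onset possible"; the second is the same for placebo.
- **Start date wholly missing.** "Do not impute completely missing AE start dates". The AE is deemed treatment-emergent directly, unless its end date shows that it was over before treatment.

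The only rule for a missing onset time is in SAP section 11.2 and concerns temporal association: "In case time of onset of AE is missing, the AE is considered temporally related" if the onset day falls between the infusion start day and three days after the infusion end day, inclusive.

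In SAP Table 8, Study Period 1 ends at Week 25 before the infusion, and Study Period 2 begins at the date and time of the first Week 25 infusion.

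**The concern.** TEAE percentages and annualized rates are the secondary safety endpoint. The first infusion day is the first exposure to each product, and the plan treats local reactions as important enough for their own virtual SOC. The boundary rule on that day should therefore be unambiguous, and it is not.

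The SAP departs from the protocol without saying so. It also sets some partial dates exactly on the boundary in order to include the events, then applies a test that a date on the boundary does not pass. And although it foresees missing onset times, it resolves them for temporal association but not for TEAE status. Read literally, an untimed first-day AE could be a temporally associated TEAE without being a TEAE, so that row of the overview table need not nest within the any-TEAE row.

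A strict reading can only lower the TEAE count. If the text is silent, the choice passes to whoever programs the flag, whereas SAP section 3 requires decisions on the primary data analysis to be made before unblinding.

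**Working it through.** The documents give no figure to reproduce; the check is of logic. I applied both boundaries to onset. (The protocol's *reported*, taken literally, is a further difference.) For illustration, the first infusion starts at 10:00. Date and time are compared where a time exists, and calendar dates where it does not.

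| Onset as recorded | SAP: onset > start | Protocol boundary: onset ≥ start |
|---|---|---|
| Same day, 11:00 | TEAE | TEAE |
| Same day, exactly 10:00 | not TEAE | TEAE |
| Same day, time missing | not TEAE | TEAE |
| Partial date imputed to that day, no time | not TEAE | TEAE |
| Imputed date stored as 00:00 | not TEAE | not TEAE |
| Next day, no time | TEAE | TEAE |
| Same day, 09:00 | not TEAE | not TEAE |

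Four things follow.

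1. The definitions differ only at the boundary. First-day AEs with a recorded time after the start are unaffected.
2. Date-only records sit on that boundary. For AEs imputed to the Week 1 date, the strict test contradicts the purpose stated in section 8.1.2.
3. An inclusive boundary is not sufficient alone: if software stores a missing time as midnight, the event still falls before a 10:00 start. A rule for missing times is also needed.
4. If the onset time is treated as missing and dates are compared with ≥, every untimed or imputed first-day case becomes a TEAE. The 09:00 case stays out.

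**Week 25.** Any AE beginning that day is after the first infusion in Week 1, so it is a TEAE under either definition. What a missing time leaves open is whether onset preceded the first Week 25 infusion (Study Period 1) or followed it (Study Period 2). For Sequence B this decides between placebo and IgPro20. Section 8.1.2 assigns Sequence B events that could belong to either product, because of missing elements, to the IgPro20 period. Its table, however, lists only day, month and year as elements. The same period question arises at the first Week 53 infusion.

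**Size.** Neither document gives the frequency of missing onset times or partial dates. If all 63 planned subjects per sequence are treated, one subject whose only Study Period 1 TEAE is such an event changes that arm's percentage by 100 × 1/63 = 1.6 points.

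**The case against.** The strongest reply is that the SAP's intent is clear. Section 8.1.2 says imputed events are to count, and a specific rule should prevail over one preposition in a general definition. The missing-time rule in section 11.2 includes the infusion day. Section 8.2 defers full derivation details to dataset specifications that are not part of these documents. With complete times, the definitions part only at the exact start of the infusion. The rule is the same in both arms, the TEAE tables are descriptive, all AEs are listed regardless, and no efficacy test is touched.

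Most of this stands, and it rules out three stronger readings that a reader might infer:

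- *First-day date-only AEs are plainly not TEAEs.* For imputed dates the SAP contradicts itself rather than excluding them. For untimed AEs it compares a date and time with an infusion start time and does not say what to do when the time is absent. Exclusion follows only if calendar dates are compared strictly.
- *The imputation has no effect.* AEs with wholly missing start dates are deemed treatment-emergent without any comparison, and Sequence B AEs imputed to the Week 25 date are already past the first infusion. The conflict is confined to partial dates set to the Week 1 start.
- *Week 25 same-day events are lost.* They stay in the overall TEAE analysis, and section 8.1.2 points to the IgPro20 period for Sequence B.

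One further objection bears on the remedy. Baseline and Week 1 are one visit, AEs are documented at Baseline, and protocol Table 14 places Week 1 AE documentation before the first infusion. Some untimed AEs on that date will have begun before treatment. That stands as a cost.

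**Conclusion.** The concern holds in a limited form. The undeclared difference between protocol and SAP is real. So is the contradiction between the strict test and the section 8.1.2 imputation for partial dates set to the Week 1 infusion date. Fully dated AEs on the first infusion day without an onset time are excluded under a strict date comparison and otherwise undetermined. At Week 25, and likewise at Week 53, only the period is unclear.

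The number of events cannot be stated; the figure of 1.6 points per subject assumes 63 treated subjects per arm and no other TEAE in that subject. The direction is known: a strict reading under-counts. Because the rule governs the secondary safety endpoint and is easily settled, it should be corrected before unblinding. It does not affect the efficacy conclusions.

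**What to change.** In SAP sections 8.3.1 and 11.2:

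- Define a TEAE as an AE with onset at or after the start of the first IMP infusion, keyed on onset rather than reporting.
- If the onset time is missing or the start date has been imputed, compare calendar dates and count the AE when its onset date is on or after the first infusion date. Treat a missing time as missing, never as midnight.
- Keep AEs documented as starting before the infusion as non-TEAE.

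In SAP section 8.1.2, state that the priority rule also covers a missing onset time, so that date-only AEs on the day of the first Week 25 or Week 53 infusion go to the period that starts that day.

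The cost is a few sentences, one comparison in the TEAE flag and a matching line in period assignment. The downside is conservative: some untimed AEs on the Baseline/Week 1 day that began before the infusion will be counted as TEAEs. How many cannot be said from the documents.

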### 11.3 Adverse Events of Special Interest (AESI)

In this study, TEEs will be treated as AESIs. The following 3 narrow standardized MedDRA queries will be utilized for TEE evaluation:

- Embolic and thrombotic events, arterial
- Embolic and thrombotic events, venous
- Embolic and thrombotic events, vessel type unspecified and mixed arterial and venous

In addition to the comprehensive search by MedDRA SMQs, the site enters their assessment in the eCRF on whether the AE is of special interest. These entries are listed but not summarized.

The potentially elevated risk of IgPro20 TEEs over placebo will be evaluated by the IDMC. The IDMC will assess whether a TEE counts towards the stopping rule. Only the TEEs counting towards the stopping rule will be included in this analysis.

TEE rates will be calculated for each treatment group, along with relative risk (IgPro20 over placebo) and associated 80% credibility intervals based on Bayesian technique [Barker et al, 2008], which accounts for the consideration of differential exposure times and the possibility of no TEEs in either treatment group. The analysis will include data from Study Period 1 and Study Period 2.

An excess of TEEs in IgPro20 over placebo will be considered if the lower limit of the 80% credibility interval for the relative risk (RR) is  $> 1.1$  (presumably an IgPro20 rate greater than 10% (relative) over placebo). In this case the IDMC may recommend stopping the trial.

Point estimates for the relative risk and the upper and lower limit of the corresponding  $(1-\alpha)$  credibility interval will be calculated as follows:

$$RR = \left( \frac{TEE_{IgPro20} + 1}{TEE_{Pbo} + 1} \times \frac{T_{Pbo}}{T_{IgPro20}} \right) \times F(2TEE_{IgPro20} + 2, 2TEE_{Pbo} + 2, 0.5)$$

$$RR_{LL\ CI} = \left( \frac{TEE_{IgPro20} + 1}{TEE_{Pbo} + 1} \times \frac{T_{Pbo}}{T_{IgPro20}} \right) \times F\left(2TEE_{IgPro20} + 2, 2TEE_{Pbo} + 2, \frac{\alpha}{2}\right)$$

$$RR_{UL\ CI} = \left( \frac{TEE_{IgPro20} + 1}{TEE_{Pbo} + 1} \times \frac{T_{Pbo}}{T_{IgPro20}} \right) \times F\left(2TEE_{IgPro20} + 2, 2TEE_{Pbo} + 2, 1 - \frac{\alpha}{2}\right)$$

With

$RR$ : Point estimate for the relative risk of experiencing a TEE under IgPro20 compared with placebo

$RR_{LL\ CI}$ : Lower limit of the  $(1-\alpha)$  credibility interval for RR

$RR_{UL\ CI}$ : Upper limit of the  $(1-\alpha)$  credibility interval for RR

$TEE_{IgPro20}$ : Total number of TEEs that count towards the stopping rule under IgPro20

$TEE_{Pbo}$ : Total number of TEEs that count towards the stopping rule under placebo

$T_{IgPro20}$ : Total observational time (days) over all subjects treated with IgPro20

$T_{Pbo}$ : Total observational time (days) over all subjects treated with placebo

$F(d_1, d_2, \alpha)$ : alpha-quantile of the F distribution with parameters  $d_1$  and  $d_2$

As the data can neither be completely cleaned nor complete at the time of IDMC analyses following the occurrence of a TEE, assumptions and derivation of total observational time are described in detail in the IDMC analysis plan.

## 11.4 Pregnancies

While pregnancy itself is not considered to be an AE or SAE, any pregnancy complication or elective termination of a pregnancy for medical reasons will be recorded as an AE or SAE as described in the protocol. If any subject becomes pregnant while on the study, the information will be included in the narratives and no separate table or listing will be produced.

## 11.5 Clinical Laboratory Evaluations

The following laboratory tests will be summarized as described in this section:

**Hematology:** hemoglobin, hematocrit, platelets, erythrocytes, leukocytes with differential counts (neutrophils, basophils, eosinophils, lymphocytes, monocytes), reticulocytes, hemoglobin A1c

**Biochemistry:** sodium, potassium, chloride, bicarbonate, blood urea nitrogen (BUN), glucose, gamma-glutamyl transferase (GGT), alkaline phosphatase, creatinine, CK, LDH, AST, ALT, aldolase

**Coagulation:** D-dimer

**Virology:** Human immunodeficiency virus (HIV-1, HIV-2), Hepatitis B virus (HBV), and Hepatitis C virus (HCV)

**Additional lab tests for hemolysis criteria:** AB0 blood group, Rh factor, direct antiglobulin test (DAT), total bilirubin, direct bilirubin, indirect bilirubin, haptoglobin, blood smear to check for spherocytosis

Laboratory data will be presented in units provided by the central laboratory.

Lab values will be summarized descriptively by visit using only values from scheduled visits.

Summaries of worst-case changes from baseline with respect to the normal range will be provided: decreases to below the normal range, changes to within the normal range or no changes from baseline and increases to above the normal range will be summarized for the worst-case post-reference visit. If a subject has a decrease to below the normal range and an increase to above the normal range during the same time interval, then the subject is counted in both the decrease to below the normal range and increase to above the normal range categories.

Separate summary tables for hematology, biochemistry, and virology laboratory tests will be produced. Changes from reference visit are produced for hematology and biochemistry only.

The denominator in percentage calculation at each scheduled visit will be based on the number of subjects with a non-missing value at each visit.

The following summaries will be provided by groups defined in Section 11:

- All laboratory values by visit
- Laboratory value changes from reference visit
- Worst-case changes from reference visit with respect to the normal range

Listings to be produced are:

- All Laboratory values, incl. changes from reference visit, values outside normal range will be flagged

